Amended Clinical Study Protocol

Drug Substance	AZD9668
Study Code	D0520C000010
Edition Number	2
Date	

A Phase II Randomised, Double-Blind, Placebo-Controlled, Parallel Group Study to Assess the Efficacy of 28 Day Oral Administration of AZD9668 in Patients with Bronchiectasis

Sponsor: AstraZeneca AB, [name]

AstraZeneca Research and Development
site representative

	Date
--	------

This submission /document contains trade secrets and confidential commercial information, disclosure of which is prohibited without providing advance notice to AstraZeneca and opportunity to object.

The following Amendment(s) and Administrative Changes are included in this amended protocol:

Amendment No.	Date of Amendment	Local Amendment No.	Date of local Amendment
1			
2			
Administrative change No.	Date of Administrative Change	Local Administrative change No.	Date of local Administrative Change

PROTOCOL SYNOPSIS

A Phase II Randomised, Double-Blind, Placebo-Controlled, Parallel Group Study to Assess the Efficacy of 28 Day Oral Administration of AZD9668 in Patients with Bronchiectasis

International Co-ordinating Investigator

[REDACTED]

Study centre(s) and number of patients planned

It is planned to enrol approximately 60 patients, in order to randomise 40 patients. This study will be conducted in Canada (approximately 6 centres) and UK (approximately 4 centres), with 2-6 patients being randomised per site. Additional sites in Europe will be considered as required.

This study has an optional pharmacogenetic research element which will be detailed in Appendix D

Study period

Estimated date of first subject enrolled

[REDACTED]

Estimated date of last subject completed

[REDACTED]

Phase of development

Phase II

Objectives

The Primary Objective is:

To investigate whether AZD9668 shows evidence of efficacy in bronchiectasis patients by investigation of:

- Absolute and percentage neutrophil cell count in the sputum
- Signs and symptoms of bronchiectasis (including effects on quality of life)

The Secondary Objectives are:

- To investigate the effect of AZD9668 on Neutrophil Elastase (NE) activity in sputum
- To investigate the effect of AZD9668 on other inflammatory markers in sputum
- To investigate the effect of AZD9668 on inflammatory markers in blood
- To investigate the safety and tolerability of 28 days' dosing with AZD9668 in bronchiectasis patients
- To confirm AZD9668 exposure in plasma and in spontaneously produced sputum
- To investigate the effect of AZD9668 on urine desmosine (marker of tissue degradation)

The Exploratory Objectives are:

- To investigate the effect of AZD9668 on other markers of tissue degradation
- To investigate the effect of AZD9668 on markers of mucus hyper-secretion
- To collect samples for possible retrospective pharmacogenetics analysis to investigate the influence of genotype on pharmacokinetics (and pharmacodynamic response where appropriate). This will not form part of the Clinical Study Report (CSR).

Study design

This is a randomised, double-blind placebo-controlled, parallel group study in patients with bronchiectasis. Forty patients will be randomised to treatment at a ratio of 1:1 (AZD9668:placebo). Patients who complete the study, will be required to attend 10 visits, some of which may be undertaken in their own home.

There will be an optional pharmacogenetics element to collect samples that may be used for the possible retrospective analysis to investigate the influence of genotype on pharmacokinetics (and pharmacodynamic response, where appropriate). Further details can be found in Appendix D.

Target patient population

Male and female (non child bearing potential) patients between 18 and 80 years, with a clinical diagnosis of idiopathic or post-infective bronchiectasis as confirmed by historical high resolution computerised tomography (HRCT) or bronchogram.

Investigational product, dosage and mode of administration

AZD9668 will be administered orally as a dose of 60 mg (2 x 30mg tablets) twice a day (b.i.d) for 28 days.

Comparator, dosage and mode of administration

Matching placebo tablets will be administered orally, two tablets, twice a day (b.i.d) for 28 days

Duration of treatment

Treatment will continue for 28 days unless any of the discontinuation criteria are met.

Outcome variable(s):

Primary variables

- Sputum neutrophils:
 - Absolute and percentage neutrophil cell count
- Signs and symptoms of bronchiectasis:
 - Bronkotest[®] diary card data
 - Weight of 24 hour sputum collection (pre-treatment versus end of treatment)
 - Quality of life as assessed by St George's Respiratory Questionnaire
 - Lung function tests: (Forced expiratory volume in one second [FEV₁], Slow vital capacity [SVC], Forced vital capacity [FVC], forced expiratory flow between 25 and 75% of forced vital capacity [FEF₂₅₋₇₅])

Secondary variables

- Safety variables
 - vital signs, ECG, haematology, clinical chemistry, urinalysis, sputum culture, reported adverse events.
- Pharmacokinetic variables
 - AZD9668 concentration in plasma and sputum
- Pharmacodynamic variables
 - NE activity in sputum (subject to the availability of validated assay)

- Other inflammatory markers in sputum, including, but not limited to (and subject to the availability of validated assays): TNF- α , IL-8, LTB-4, IL-6, IL-1 β , RANTES, MCP-1
- Blood inflammatory markers, including, but not limited to (and subject to the availability of validated assays): differential cell count [absolute and percentage neutrophils], TNF- α , IL-8, high sensitivity CRP, Amyloid-A, IL-6, IL-1 β
- Urine desmosine (marker of tissue degradation)
- **Exploratory variables**
 - Plasma desmosine and sputum hydroxyproline (markers of tissue degradation)
 - MUC5AC in sputum (marker of sputum hyper secretion)

Subject to the availability of validated assays.

- Retrospective pharmacogenetic analysis to investigate the influence of genotype on the pharmacokinetics of AZD9668 (and pharmacodynamic response where appropriate). Further details can be found in Appendix D.

Statistical methods

The primary outcome variables will be compared between AZD9668 and placebo using an analysis of variance model with fixed factors treatment and country (or centre) and using baseline as a covariate. As the study is exploratory in nature, a p-value of <0.1 will be considered significant. A 2-sided 90% confidence interval will be constructed for the treatment difference and p-values given. For variables with a skewed distribution, data may be log-transformed prior to analysis or a non-parametric test (Wilcoxon rank sum) used instead. The primary outcome variable analyses will be carried out on the Efficacy Analysis Set.

All other data will be summarised and listed.

There will not be an interim analysis for this study.

Pharmacokinetic analyses will be carried out by, or under the guidance of, the [REDACTED] group within AstraZeneca

TABLE OF CONTENTS	PAGE
TITLE PAGE	1
PROTOCOL SYNOPSIS.....	2
TABLE OF CONTENTS.....	6
LIST OF ABBREVIATIONS AND DEFINITION OF TERMS	11
1. IMPORTANT MEDICAL PROCEDURES TO BE FOLLOWED BY THE INVESTIGATOR	15
1.1 Medical emergencies and AstraZeneca contacts	15
1.2 Overdose	16
1.3 Pregnancy.....	16
1.3.1 Maternal exposure.....	16
1.3.2 Paternal exposure	17
2. INTRODUCTION	17
2.1 Background.....	17
2.2 Research hypothesis.....	18

Table 1	Primary outcome variables	20
Table 2	Secondary outcome variables	21
Table 3	Table of study assessments.....	25
Table 4	Spontaneous sputum sample summary.....	28
Table 5	Identity of investigational products	36

Table 6	Laboratory Parameters.....	45
Table 7	Bronkotest [®] Diary Card variables	48
Table 8	Volume of blood to be drawn from each patient	53

LIST OF FIGURES

Figure 1	Study design	23
----------	--------------------	----

LIST OF APPENDICES

Appendix A	Signatures (Not Applicable)
Appendix B	Additional Safety Information
Appendix C	IATA 6.2 Guidance document
Appendix D	Optional Genetic Research
Appendix E	St George’s Respiratory Questionnaire (SGRQ-C)
Appendix F	Bronkotest [®] Diary Card

LIST OF ABBREVIATIONS AND DEFINITION OF TERMS

The following abbreviations and special terms are used in this study protocol.

Abbreviation or special term	Explanation
AE	Adverse event (see definition in Section 7.3.1)
ALT	Alanine aminotransferase
AMOS	Astra Zeneca database
AST	Aspartate aminotransferase
ATC	Anatomical Therapeutic Chemical Classification of Drug
AUC	Area under the plasma concentration time curve from time zero to infinity
AUC ₍₀₋₂₄₎	AUC from time zero to 24 hours post-dose
AUC _{(0-24),ss}	AUC ₍₀₋₂₄₎ at steady state
AZ	AstraZeneca
BAL	Bronchoalveolar lavage
b.i.d	Twice daily dosing (latin)
CL/F	Apparent plasma clearance following oral drug administration
CL/F _{,ss}	CL/F at steady state
CL _R	Renal clearance
CL _{R,ss}	CL _R at steady state
C _{max}	Observed peak or maximum plasma concentration following drug administration
C _{max,ss}	C _{max} at steady state
CRR	Clinical Research Region
COPD	Chronic Obstructive Pulmonary Disease
CPK	Creatinine phosphokinase
CPMP	Committee for Proprietary Medicinal Products
CRF	Case report form
CRP	C-reactive protein
CSR	Clinical study report
CYP	Cytochrome P450
DAE	Discontinuation due to Adverse Event
DMP	Data management plan
DMPK	Drug metabolism and pharmacokinetics

Abbreviation or special term	Explanation
DNA	Deoxyribonucleic acid
DQF	Data query form
ECG	Electrocardiogram
Ecode	Enrolment code
EDTA	Ethylenediamine tetra-acetic acid
EU	European union
Fe ₍₀₋₄₈₎ (%)	Percentage of the dose excreted as unchanged parent in the urine from time zero to 48 hours
Fe _{(0-48),ss} (%)	Fe ₍₀₋₄₈₎ (%) at steady state
FEF25-75	forced expiratory flow between 25 and 75% of forced vital capacity
FEV ₁	Forced expiratory volume in the first second
FSH	Follicle-stimulating hormone
FVC	Forced vital capacity
GARNET	Global application for reconciliation and narrative transcription
GCP	Good Clinical Practice
GGT	Gamma-glutamyltransferase
GMP	Good Medical Practice
GRand	Global randomisation system
hCG	Human chorionic gonadotropin
HELC	AstraZeneca Human Exposure Limits Committee
HIV	Human immunodeficiency virus
HRCT	High Resolution Computerised Tomography
IB	Investigator brochure
ICH	International Conference on Harmonisation
ICS	Inhaled corticosteroids
IL-1 β	Interleukin 1 beta
IL-6	Interleukin 6
IL-8	Interleukin 8
International Co-ordinating investigator	If a study is conducted in several countries the International Co-ordinating Investigator is the Investigator co-ordinating the investigators and/or activities internationally.
IP	Investigational product
LABA	Long-acting β agonists

Abbreviation or special term	Explanation
LAMA	Long-acting muscarinic antagonist
LDH	Lactate dehydrogenase
LFT	Liver function test(s)
LIMS	Laboratory information management system
LLN	Lower limit of normal
LLOQ	Lower Limit of Quantification
LTB ₄	Leukotriene B4
MAD	Multiple ascending dose
MC	Marketing Company
MCH	Mean cell haemoglobin
MCHC	Mean cell haemoglobin concentration
MCP-1	Monocyte chemoattractant protein
MCV	Mean cell volume
MedDRA	Medical Dictionary for Drug Regulatory Affairs
MID	Minimal clinically important difference
MUC5AC	Mucin 5AC
NCR	No carbon required
NE	Neutrophil Elastase
NOAEL	No observed adverse effect level
NOEL	No observed effect level
OAE	Other Significant Adverse Event (ie, adverse events of particular clinical importance, other than SAEs and those AEs leading to discontinuation of the patient from study treatment; see definition in Section 12.2.4
pCRF	Paper CRF
PD	Pharmacodynamic(s)
PEF	Peak Expiratory flow
PK	Pharmacokinetic(s)
PoP	Proof of principle
prn	Pro re nata (latin) – “As and when required”
PRO	Patient reported outcome
QT	ECG interval measured from the beginning of the Q wave (or the R wave if Q is missing) to the end of the T wave; the time interval of ventricular depolarisation and repolarisation

Abbreviation or special term	Explanation
QTc	Corrected QT
R&D	Research and development
RAMOS	Remote AMOS
RANTES	Regulated on activation, normal T cell expressed and secreted
RV	Residual Volume
SABA	Short-acting β agonists
SAD	Single ascending dose
SAE	Serious adverse event (see definition in Section 7.3.2).
SAMA	Short-acting muscarinic antagonist
SAP	Statistical analysis plan
S-CPK-MB	Serum creatinine phosphokinase, muscle and brain
SD	Standard deviation
SGRQ-C	St Georges Respiratory Questionnaire for COPD patients
SOP	Standard operating procedure
SVC	Slow Vital Capacity
$t_{1/2}$	Half-life
$t_{1/2,ss}$	Half-life at steady-state
T ₄	Thyroxine
t_{max}	Time to reach observed peak or maximum concentration following drug administration
$t_{max, ss}$	t_{max} at steady state
TNF α	Tumour necrosis factor alpha
TSH	Thyroid stimulating hormone
UK	United Kingdom
ULN	Upper limit of normal
UV	Ultraviolet
V _z /F	Apparent terminal volume of distribution following extra-vascular dosing
V _z /F _{,ss}	V _z /F at steady state
WBDC	Web Based Data Capture
WHO	World health organisation

1.2 Overdose

For the purpose of this study an overdose is defined as any dose of investigational product above that which is mandated within the protocol. There is no specific antidote to AZD9668; in cases of overdose, appropriate supportive measures should be undertaken.

The Clinical Study Overdose Report Form will be used in this study:

- An Overdose with associated SAEs is recorded as the SAE diagnosis/symptoms on the relevant AE forms in the CRF only.
- An Overdose with associated non-serious AEs is recorded as the AE diagnosis/symptoms on the relevant AE forms in the CRF and on the separate AZ “Clinical Study Overdose Report Form”.
- An Overdose without associated symptoms is only reported on the separate AZ “Clinical Study Overdose Report Form”

The clinical study overdose report form should be sent through to the appropriate Patient Safety Data Entry Site (DES) within 30 days of the Investigator becoming aware.

1.3 Pregnancy

All outcomes of pregnancy must be reported to AstraZeneca.

1.3.1 Maternal exposure

Pregnancy itself is not regarded as an adverse event unless there is a suspicion that the investigational product under study may have interfered with the effectiveness of a contraceptive medication. Congenital abnormalities/birth defects and spontaneous miscarriages should be reported and handled as SAEs. Elective abortions without complications should not be handled as AEs. The outcome of all pregnancies (spontaneous miscarriage, elective termination, normal birth or congenital abnormality) must be followed up and documented even if the patient was discontinued from the study.

If any pregnancy occurs in the course of the study, then investigators or other site personnel inform appropriate AstraZeneca representatives immediately but no later than the end of the next business day of when he or she becomes aware of it. The designated AstraZeneca representative works with the investigator to ensure that all relevant information is provided to the appropriate Patient Safety Data Entry Site (DES) within 30 calendar days.

The Pregnancy Outcome Report, SOP-330-G T02 is used in this study.

The Pregnancy Outcome Report, part 1, is used to report the pregnancy and the Pregnancy Outcome Report, part 2, is used to report the outcome of the pregnancy. These reports should be sent through to the appropriate Patient Safety Data Entry Site (DES) within 30 days of the Investigator becoming aware.

1.3.2 Paternal exposure

The outcomes of any conception occurring from the date of the first dose until 3 months after the last dose must be followed up and documented.

Male patients must refrain from fathering a child during the study and **three** months following the last dose, since the potential for chromosomal aberrations in male gametes, and possible teratogenic effects thereof, has not yet been thoroughly investigated.

Pregnancy of the patients partners is not considered to be an adverse event. However, the outcome of all pregnancies (spontaneous miscarriage, elective termination, normal birth or congenital abnormality) must be followed up and documented.

2. INTRODUCTION

2.1 Background

AZD9668 is a potent, oral, selective, reversible inhibitor of human neutrophil elastase (NE). It is primarily being developed as a possible therapeutic agent both for symptomatic treatment as well as disease modification in COPD.

NE is a serine protease found in high levels in neutrophils. NE is able to degrade extracellular matrix and proteins leading to long-term destruction of the lung parenchyma. Inhibition of neutrophil elastase therefore has the potential to inhibit this proteolytic destruction raising the possibility of disease modification. A number of clinical and experimental observations indicate that NE plays a pivotal role in COPD, which renders this enzyme a compelling target for drug discovery. Overall, the findings from these studies suggest that an NE inhibitor can be expected to have a beneficial effect on the inflammation, mucus hyper-secretion and matrix degradation characteristic of COPD (Smith et al 2001, Ohbayashi 2002) and thereby provide a therapeutic benefit in terms of symptom control as well as slowing the progressive decline in lung function, both in stable disease and during exacerbations. It could also be of benefit in other airway diseases characterised by neutrophilic inflammation such as bronchiectasis and cystic fibrosis.

Orally administered AZD9668 produced a dose-dependent inhibition of human NE-induced lung haemorrhage in the mouse. Mice exposed to cigarette smoke and treated with AZD9668 showed a significant reduction in total number of cells and neutrophils and IL1- β , compared to vehicle treated smoke exposed mice, indicating the possibility of inhibiting endogenously released NE with this drug.

AZD9668 was well tolerated in rat and dog toxicity studies. In a dog 28-day toxicity study minor haematological abnormalities and a slight QT-prolongation (9%) at a high dose was observed. These however occurred at plasma levels clearly above the expected human exposure range. Mutagenicity tests indicated that AZD9668 does not pose a significant genotoxicity risk.

A first administration to man, Phase I, randomised, double blind, placebo-controlled, 2-part study to assess the safety and tolerability, and pharmacokinetics of single and multiple oral doses of AZD9668 in healthy volunteers has been completed. In the single ascending dose part of the study, AZD9668 was administered at doses of 2 mg, 10 mg, 30 mg, 60 mg, 120 mg and 150 mg with 36 patients receiving the active drug and 12 patients receiving the placebo. In the multiple ascending dose part of the study the drug was given in doses of 30 mg, 70 mg and 120 mg once daily for 8 days with 18 patients receiving the active drug and 9 the placebo. Overall, AZD9668 was well tolerated except for the occurrence of headaches at the highest doses tested. No laboratory abnormalities of any concern or QT prolongation were noted in any of the patients. The PK data from this study is detailed in Section 4.2.

A further safety and tolerability study of AZD9668 in Caucasian and Japanese healthy volunteers, at doses of up to 70 mg b.i.d has been conducted, and a study of tolerability of AZD9668 in COPD patients at a dose of 60 mg b.i.d. has been initiated. Emerging PK and safety data from the Caucasian/Japanese healthy volunteers study give no concern to proceed to studies with b.i.d. dosing in patient groups with this drug.

Details of pre-clinical and clinical pharmacology, toxicity and safety and tolerability of AZD9668 are given in the Investigators Brochure (IB).

The current study is a proof-of-principle (PoP) study in patients with bronchiectasis to see if it is possible to demonstrate that AZD9668 inhibits NE activity and some of its downstream effects. Bronchiectasis is a pathological description of a progressive and debilitating disease in which airways become permanently dilated as the result of inflammatory-related destruction of structural components of the bronchial wall (Barker 2002). As in COPD the airway inflammation in bronchiectasis is characterised by neutrophilic inflammation. Bronchiectasis is chosen as an “exaggerated model” of COPD (see Section 2.3), as NE levels in the sputum are consistently higher in this condition than in stable COPD.

AstraZeneca may perform genetic research in the AZD9668 clinical development programme to explore how genetic variations may affect the clinical parameters associated with AZD9668. Collection of DNA samples from populations with well described clinical characteristics may aid in the identification of future drug targets and projects to validate identified targets. Further details of the optional pharmacogenetic component of this study can be found in Appendix D.

2.2 Research hypothesis

The research hypothesis is that the neutrophil elastase inhibitor AZD9668 shows an effect on the inflammatory markers and signs and symptoms (including quality of life) in patients with bronchiectasis and is safe and well tolerated when given orally at a dose of 60 mg b.i.d. for 28 days.

2.3 Rationale for conducting this study

AZD9668 is primarily being developed as a treatment for COPD. So far it has been found to be safe and well tolerated in healthy volunteers. In order to determine if a neutrophil elastase

inhibitor has potential benefit as a treatment for COPD, a one-month study in patients with bronchiectasis is planned, as an “exaggerated model” of COPD for this target mechanism.

COPD and bronchiectasis share many features; both are characterised by a primarily neutrophilic inflammation, both exhibit varying degrees of fixed airway obstruction, and both experience acute infective exacerbations. There is considerable overlap between the conditions: surveys have shown that 30% of COPD patients diagnosed in general practice, and 50% seen in hospital clinics, have some degree of bronchiectasis on high resolution computerised tomography (HRCT) scanning. In both conditions increased levels of NE activity are seen in the sputum or bronchoalveolar lavage (BAL), but the levels are considerably higher in bronchiectasis, giving a larger window to show a pharmacodynamic effect of an NE inhibitor. Hence, this condition is considered a suitable ‘exaggerated model’ of COPD, which could be used in PoP studies with an opportunity to see greater changes in biomarkers and clinical parameters such as sputum colour and volume. In addition, it might also make it possible to demonstrate an effect of NE inhibition with a smaller number of patients, than if the study was conducted in patients with COPD. Although a 2-week study would be expected to be sufficient to demonstrate changes in NE activity, a 4-week study offers an increased likelihood of observing changes in clinical outcomes.

2.4 Benefit/risk and ethical assessment

Patients with COPD are the target population for the NE inhibitor AZD9668. The main purpose of this study is to establish the proof-of-principle that the neutrophil elastase inhibitor AZD9668 shows some effect on the inflammatory markers and signs and symptoms in patients with bronchiectasis, so that one could proceed with confidence to longer-term proof-of-concept studies in COPD patients. It is also intended to obtain further safety/tolerability data prior to proof-of-concept and dose finding studies in COPD patients.

A detailed assessment of the overall risk/benefit of developing a NE inhibitor in COPD is given in the IB. COPD presents an area of high unmet medical need, and there is considerable evidence to indicate that NE presents a compelling target for drug development. In this study bronchiectasis is chosen as an “exaggerated model” of COPD with regard to neutrophilic inflammation and NE activity mediated changes, so that proof that an NE inhibitor is effective in patients can be established in principle, by exposing a fewer number of patients than if the study was conducted in patients with stable COPD. Furthermore, the study could show that a NE inhibitor could be useful in bronchiectasis *per se*.

So far, safety/tolerability and PK data are available in healthy volunteers up to 150 mg as a single dose and up to 120 mg daily for 8 days, and 70 mg b.i.d. as multiple doses. Detail of the PK and the rationale for choosing a dose of 60 mg b.i.d. for this study are detailed in Section 4.2 and the IB.

To mitigate the risks identified in the pre-clinical toxicology studies, haematological and biochemical parameters including evidence for haemolysis will continue to be monitored. Although no significant QT abnormalities were observed in the healthy volunteers studies, patients with a prolonged QT_c value will not be entered into this study. Also, only patients

with normal renal function and normal haematological parameters will be entered into the study.

For an overall risk benefit assessment of developing a NE inhibitor in COPD, see the Investigator's Brochure.

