5. PATIENT SELECTION CRITERIA

Patient population should be selected without bias.

Investigator(s) must keep a record of patients who entered pre-trial screening but were never enrolled eg, patient screening log. Each patient must meet all of the inclusion criteria and none of the exclusion criteria for this study. Under no circumstances can there be exceptions to this rule.

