5.2 Exclusion criteria

Patients must not enter the study if any of the following exclusion criteria are fulfilled

1. Involvement in the planning and/or conduct of the study (applies to both AstraZeneca staff and/or staff at the study site)
2. Previous randomization of treatment in the present study
3. Participation (defined as administration of at least one dose of investigational product) in another clinical study within 12 weeks of Visit 1.
4. Bronchiectasis associated with a generalised immunodeficiency disorder, where manifestations other than bronchiectasis predominate
5. Concomitant diagnosis of significant pulmonary disease other than bronchiectasis or COPD, including symptomatic asthma and allergic bronchopulmonary aspergillosis
6. An FEV₁ of <30% of predicted normal at Visit 1
7. Any ECG abnormality at Visit 1 (including a QTc interval of >450 msec for males and >470 msec for females, or any arrhythmia) which in the opinion of the investigator may put the patient at risk or interfere with study assessments.
8. An acute exacerbation (defined as an increase in respiratory symptoms requiring hospitalisation and/or a course of oral glucocorticosteroids and/or antibiotics, either prescribed or self administered); or acute respiratory infection (upper or lower) requiring oral steroids or antibiotics in the 6 weeks prior to Visit 2

9. Other acute infections requiring treatment in the 4 weeks prior to Visit 2
10. Use of prohibited medications as detailed in Section 6.5
11. A past history of or current clinical or laboratory evidence of renal disease, or a calculated creatinine clearance (Cockcroft-Gault formula) of ≤ 70 ml/min at Visit 1
12. Any other clinical disease or disorder (including insulin dependent diabetes) which, in the opinion of the investigator, may either put the patient at risk because of participation in the study, or may influence the results of the study, or the patient's ability to participate in the study
13. History of excessive alcohol consumption or chronic alcohol induced disease
14. Donation of >1350 mL of blood in the 12 months or 500 mL of blood in the 3 months before the end of the study
15. Suspected or known risk of the patient transmitting HIV, Hepatitis B or C
16. Scheduled in patient surgery or hospitalisation during the course of the study

Criteria relating specifically to the optional pharmacogenetics component can be found in Appendix D.

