5.4 Withdrawal of patients

5.4.1 Criteria for discontinuation from the study

Patients may be discontinued from study treatment and assessments at any time. Specific reasons for discontinuing a patient are:

- Voluntary discontinuation by the patient who is at any time free to discontinue his/her participation in the study, without prejudice to further treatment
- Risk to patients as judged by the investigator and/or AstraZeneca
- Severe non-compliance to protocol as judged by the investigator and/or AstraZeneca
- Incorrectly enrolled patients
- Patient lost to follow-up
- Non-compliance to study medication (compliance rate of $\leq 80\%$ following drug accountability at Visit 3)
- Change in QTc >60 msec from baseline value or QTc >500 msec, confirmed by repeat ECG
- Withdrawal of informed consent to the use of biological samples **collected as an integral part of the study**, see Section 8.5
- An ALT / AST level $\geq 3 \times \text{ULN}$ (confirmed on repeat sample) or any pattern of liver function test (LFT) abnormalities giving Investigator or AZ cause for concern
- Evidence of haemolysis as evidenced by the following:
 - Reticulocyte count of over 5%, **and**At least two of the following:
 - a drop in haemoglobin below 10.5 g/dL
 - decrease of 25% in haptoglobin. (The value post-dose to be compared with the average of two pre-dose values. The value should also be 15% below LLN).
 - increase of 25% in unconjugated bilirubin or lactate dehydrogenase (LDH). (The value post-dose to be compared with the average of two pre-dose values. The value should also be 15% above ULN).
- A platelet count of below $80 \times 10^9/\text{L}$ confirmed by a repeat test (in the absence of obvious platelet clumping in a peripheral blood film).

Specific reasons for discontinuing a patient from the genetic research are detailed in Appendix D:

- Withdrawal of consent for genetics research. A patient may withdraw from this genetic research at any time, independent of any decision concerning participation in other aspects of the main study described in this protocol. Voluntary discontinuation by the patient will not prejudice further treatment.

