6.2 Patient enrolment and randomization

The principal investigator will:

1. Obtain signed informed consent from the potential patient before any study specific procedures are performed.
2. Assign potential patient a unique enrolment number, beginning with “E0001001 (EXXXYYYY)” where XXXX reflects the centre number and YYY will be allocated sequentially to enrolled patients at each centre.
3. Determine patient eligibility. See Sections 5.1 and 5.2
4. Assign eligible patient unique randomization code (patient number), beginning with “001”.

Randomisation codes will be computer generated by AstraZeneca R&D using the AstraZeneca Global Randomisation System (GRand). Patients who are withdrawn for any reason other than adverse events will be replaced as the aim is to achieve 40 evaluable patients. Randomization numbers should not be re-used.

Randomization codes will be assigned strictly sequentially as patients are eligible for randomization (Visit 2).

If a patient discontinues participation in the study, then his/her enrolment/randomization code cannot be reused.

If patients have discontinued after randomisation into the study then they cannot re-enter into the study.

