7.3.7 ECG

At Visits 1, 2, 3, 4 and 5, a resting 12 lead ECG will be performed as detailed in Table 3. The ECG will be performed at site according to local procedure.

ECGs will be recorded in the supine position after the patient has rested for 10 minutes. Only overall evaluation by the investigator will be captured in the pCRF. Any abnormalities (including QTc values) should be reviewed by a cardiologist or appropriately qualified physician.

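### Section 2.4 promises that no patient with a prolonged QTc will be entered, but exclusion 7 applies its QTc limits only at the investigator's discretion

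*Protocol*

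**What the plan says.** The benefit/risk assessment (Protocol, Section 2.4) has a paragraph on how the risks seen in the toxicology studies are contained. One of its measures is that "patients with a prolonged QT_c value will not be entered into this study". The section does not say what counts as prolonged.

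The rule that sites apply is exclusion 7 in Section 5.2. It opens with "Any ECG abnormality at Visit 1 (including a QTc interval of >450 msec for males and >470 msec for females, or any arrhythmia", closes the bracket, and goes on: "which in the opinion of the investigator may put the patient at risk or interfere with study assessments".

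Eligibility is decided from Section 5. Section 6.2 tells the investigator: "Determine patient eligibility. See Sections 5.1 and 5.2". The opening of Section 5 adds: "Each patient must meet all of the inclusion criteria and none of the exclusion criteria for this study".

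Three other provisions touch the same ground:

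- Exclusion 12 covers any other disease or disorder "which, in the opinion of the investigator, may either put the patient at risk because of participation in the study", or that may affect the results or the patient's ability to take part.
- Section 7.3.7 says of the ECGs: "Any abnormalities (including QTc values) should be reviewed by a cardiologist or appropriately qualified physician".
- Section 5.4.1 lists, among the reasons for discontinuation: "Change in QTc >60 msec from baseline value or QTc >500 msec, confirmed by repeat ECG".

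**The concern.** The two sections describe different safeguards. Section 2.4 tells an ethics committee or regulator that a prolonged QTc keeps a patient out. Exclusion 7 tells the site that a QTc above the limit is one kind of ECG abnormality, to be weighed by the investigator. Since Section 2.4 is not an eligibility rule and names no threshold, its promise takes effect only as far as exclusion 7 carries it.

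The stake is patient safety and the accuracy of the benefit/risk statement. Section 2.1 reports a slight QT prolongation in the 28-day dog study. Multiple dosing in the first-in-man study lasted 8 days in healthy volunteers, whereas this trial doses patients aged up to 80 for 28 days. With about 10 centres, a discretionary limit can also be applied differently from site to site.

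**Working it through.** The protocol has no figure to reproduce here, so the check sets the texts side by side.

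**1. What Section 2.4 requires.** Prolonged QTc means not entered. There is no exception and no threshold.

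**2. What exclusion 7 requires.** The main noun is an ECG abnormality at Visit 1. The bracket says what that includes: QTc above 450 msec (males), QTc above 470 msec (females), or any arrhythmia. The clause after the bracket qualifies the main noun, so it governs everything in the bracket. The criterion is met only if both hold:

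- (i) an abnormality is present; and
- (ii) in the investigator's opinion it may either endanger the patient or disturb the assessments.

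**3. Whether the drafting intends a hard limit.** The same list sets hard limits without an opinion clause: FEV₁ below 30% of predicted (exclusion 6) and creatinine clearance of 70 ml/min or less (exclusion 11). Exclusion 7 is not written that way.

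**4. A test case.** Section 2.4 defines no limit, so take exclusion 7's own limits as the meaning of prolonged. A man with a Visit 1 QTc of 480 msec is 480 − 450 = 30 msec over.

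- If the investigator sees a possible risk, or possible interference with assessments, he is excluded and the two sections agree.
- If the investigator sees neither, exclusion 7 is not met and he can be entered. Section 2.4 says he will not be.

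**5. Whether another rule closes the gap.**

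| Provision | Acts at entry? | Excludes on QTc alone? |
|---|---|---|
| Inclusion 5 (normal laboratory values) | Yes | No, it concerns laboratory values |
| Exclusion 12 | Yes | No, it also rests on investigator opinion |
| Section 7.3.7, specialist review | At any ECG | No, it asks for review only |
| Section 5.4.1, QTc stopping rule | No, after entry | Not an entry rule |

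None of them closes it.

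**6. How many patients.** The protocol gives neither a QTc distribution nor the frequency with which investigators would admit a patient above the limits. Assume, for scale only, that 0% to 5% of the roughly 60 enrolled are above the limits and would still be entered: 0 × 60 = 0 and 0.05 × 60 = 3. The lower end is 0 because exclusion 7 allows every such patient to be excluded.

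**The case against.** The strongest reply is that the safeguard is there. Exclusion 7 names explicit QTc limits, and the threshold for acting on them is low: the investigator need only think the abnormality may matter, on either of two grounds. The man at 480 msec starts 500 − 480 = 20 msec below the stopping value, and ECG is a safety variable, so an investigator could well exclude him on the second ground if not the first. This stands. A reader might infer that the safeguard is absent, or that anyone above the limits can simply be entered. The protocol supports neither inference: entry needs a judgement that neither condition applies.

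A second reply is that the bracket names values that always count as a risk. That reading is possible but strained. It would also make every arrhythmia an automatic exclusion and leave the opinion clause with nothing to do for the items listed. At best the criterion is ambiguous.

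A third reply is that other protections limit the harm. This also stands. Abnormal ECGs should get specialist review. The sponsor as well as the investigator may stop a patient for risk, and confirmed QTc changes lead to discontinuation. The dog finding was slight (9%), at a high dose and clearly above expected human exposure, and no QT prolongation was noted in the first-in-man study.

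**Conclusion.** The inconsistency is real and minor. Section 2.4 states a firm bar, while the only QTc entry rule is discretionary, and no other entry criterion makes up the difference. A patient above 450 msec (male) or 470 msec (female) whom the investigator judges to meet neither condition can be entered.

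This rests on two readings: that exclusion 7's limits are what Section 2.4 means by prolonged, and that the opinion clause governs the bracket. Both are the natural readings, though neither is spelled out.

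The number affected is unknown. On the stated assumption it is 0 to 3 of about 60 enrolled, and the conclusion does not depend on that range. The efficacy analysis is unaffected.

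**What to change.** Split exclusion 7 into two parts:

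- (a) QTc above 450 msec (males) or above 470 msec (females) excludes on its own, at Visit 1 or on the pre-dose Visit 2 ECG if that is available before randomisation.
- (b) Any other ECG abnormality, including an arrhythmia, excludes if the investigator considers it a possible risk to the patient or a possible source of interference with the assessments.

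The Visit 2 wording is needed because Table 3 repeats both the ECG and the eligibility check before dosing at that visit. A reader might think that a hard limit at Visit 1 alone would make Section 2.4 true, but a patient first found above the limit at Visit 2 would still get through.

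The cost is an amendment to one criterion. No new procedure is needed, since both ECGs are already scheduled. There may be a few more screen failures: under the assumption above, 0 to 3 patients, or 0% to 3/20 = 15% of the 60 − 40 = 20 losses already planned between enrolment and randomisation.

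Softening the sentence in Section 2.4 to match exclusion 7 would also remove the inconsistency, but it would give up the firm safeguard.
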